3 INVESTIGATIONAL PLAN

3.1 Study Design

This is a multicenter, parallel group, randomized, double-blind, placebo-controlled, trial with clinical endpoint comparing Podofilox Topical Gel 0.5% to Condylox® Gel 0.5% and a matching placebo. The study will be conducted among adult male and female patients with external anogenital warts.

All the study related procedures will be conducted only after written informed consent is obtained at the Screening visit, which will occur up to 14 days prior to the Baseline (Days -14 to -1). During the Screening visit, the Investigator will record subject's demographics, medical history, review concomitant medication, identifying any prohibited therapies that subject receives.

The Investigator will assess vital signs and perform physical examination identifying any clinically significant abnormalities that may prevent subject from participation in the study. Laboratory samples will be collected, including HIV, Hepatitis B&C, urine pregnancy tests (UPT) for women of childbearing potential and Syphilis (if required by applicable local regulations).

The Investigator will confirm the diagnosis of External Anogenital Warts (EAW) and the absence of contraindications specified in the exclusion criterion 5 during the visual examination. The biopsy of skin lesions will be performed per the discretion of the Investigator for microscopic verification of the diagnosis of EAWs.

Once the results of Screening assessments are obtained, suggesting that the subject is eligible for entering the study, the Baseline visit (Day 0) will take place. During this visit, the Investigator will identify any AEs that occurred from the last visit, review concomitant and prohibited therapies, perform vital signs and physical examination. Those subjects who qualify for entering the study will be randomized to one of the following arms in a ratio of 3:3:1:

- Arm 1 (Test product): Subjects in this arm will receive test formulation of Podofilox Topical Gel 0.5% (Hyloris Developments SA)
- Arm 2 (Reference Listed Drug [RLD]): Subjects in this arm will receive RLD Condylox® Gel 0.5%
- Arm 3 (Placebo): Subjects in this arm will receive a matching vehicle

Randomization and study drug kit number assignment will be performed using an Interactive Response System (IRT).

EAWs will be inspected and the count will be captured in the source worksheet and electronic Case Report Form (eCRF). The Investigator will assess the baseline level of Local Application Site Reactions, recording the scores on the Local Application Site Reactions Scale.

During the inspection, study physician (Principal Investigator (PI), or Sub-Investigator) will train the subject on proper application of the study drug using the demonstration tube (contains vehicle of the study drug) and applicator. The subject will be trained to apply the study drug to the surface of the warts at a proper amount (not to exceed 0.5 g per day or 0.25 g per application), avoiding unaffected and wounded skin areas, and to let the gel dry completely before allowing the return of opposing skin surfaces to their

Confidential Page 25 of 59

normal positions. Mirrors are to be used to facilitate the process of application. Subjects will be instructed to not use the study drug in the vagina or in the rectum, and remove medication from any areas that experience stinging or burning immediately upon application. A visual representation of this quantity will be showed to the subjects.

The subject will also be trained on Subject Diary Card completion and contraception methods. The subject will be given a kit of study drug, mirror and a Subject Diary Card to capture application details, and acknowledge any changes in skin reactions, other AEs and concomitant medications during the intervening time between the site visits.

On the following day after the Baseline visit (Day 1) the subject will apply the study drug on EAWs following the recommendations given at the training. The treatment phase will consist of four weekly treatment cycles at a maximum, during which the drug will be applied twice a day (in the morning and at the bedtime) for 3 consecutive days, then discontinuing for 4 consecutive days. Study drug will thus be applied only on Days 1, 2, 3, 8, 9, 10, 15, 16, 17, 22, 23 and 24.

Study visits will occur on the seventh (7) day of each treatment cycle: on Day 7 (Week 1), Day 14 (Week 2), Day 21 (Week 3), and Day 28 (Week 4). Primary endpoint (total disappearance of all warts within all treated areas) will be evaluated during each of these visits. In case the primary endpoint is reached at any of the visits following Baseline, it will be considered as End of Study (EOS) visit – the Investigator will perform physical examination and repeat urine pregnancy test, and subject's participation will be considered completed. If reduction of warts is absent or incomplete, a new treatment cycle will be initiated for a maximum of four cycles in total for the subject.

During each study visit, the Investigator will collect vital signs, evaluate EAWs for healing, capturing the count, record Local Application Site Reactions and adverse events (AEs), assess Subject Diary Card completion and subject's compliance with the study drug application, review concomitant medication and confirm that there were no prohibited therapies applied from the last visit.

In the event the primary endpoint (total disappearance of all warts within all treated areas) has been achieved, this visit will be considered End of Study (EOS) visit. In case a subject discontinues prematurely, the Investigator will conduct an Early Termination (ET) visit, capturing the reason for discontinuation and performing assessments of EOS visit.

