5.8 Treatment Compliance

Treatment compliance will be assessed by the Investigator based on Subject Diary Card completion at each study visit following the Baseline. Compliant subjects are defined as those who have completed at least 75% and no more than 125% of study drug applications until treatment success or for a maximum of four cycles of treatment.

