6.3.2 Visit 2: Baseline Visit (Day 0)

- Adverse Events Assessment
- Concomitant and Prohibited Therapies Review
- Assessment of Vital Signs
- Physical Examination
- Urine Pregnancy Test
- Visual Inspection of EAWs
- Assessment of Local Application Site Reactions
- Eligibility Criteria Check
- Randomization
- Study Drug Dispensation
- Subject Diary Card Dispensation
- Training on Study Drug Application
- Training on Subject Diary Card completion and contraception methods
- Schedule next visit to occur within window

6.3.3 Visits 3-6 (Day 7 [Week 1], Day 14 [Week 2], Day 21 [Week 3], and Day 28 [Week 4])

The following procedures will be performed:

- Subject Diary Card Return, Review and Dispensation
- Adverse Events Assessment
- Concomitant and Prohibited Therapies Review
- Assessment of Vital Signs

Confidential Page 38 of 59

- Assessment of Local Application Site Reactions
- Visual Inspection of EAWs. In the case there is a total disappearance of all warts within all treated areas at visits 2, 3, 4, or 5, this visit will be considered an End of Study (EOS) visit. In the case where reduction of warts is absent or incomplete, a new treatment cycle will be initiated for a maximum of four cycles in total for the subject.
- Study Drug Return and Accountability
- Study Drug Dispensation

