6.3.4 End of Study / Early Termination (EOS/ET) visit

The visit at which "treatment success" has been achieved will be considered EOS visit.

If "treatment success" has not been achieved through the EOS/ET visit (Day 28±5 [Week 4]), then the subject will be considered "treatment failure" and EOS activities will be performed. Similarly, if the Investigator assesses the subject's condition at any time and determines that the subject's condition has worsened to the degree that it is unsafe for the subject to continue in the study, the subject may be discontinued from the study as "treatment failure". ET visit procedures will be performed, and an alternative treatment will be advised at the Investigator's discretion.

Subjects discontinuing from the study sooner than the Day 28 visit will undergo the ET visit as soon as possible.

Following activities will be performed at EOS/ET visit:

- Subject Diary Card Return and Review
- Adverse Events Assessment
- Concomitant and Prohibited Therapies Review
- Assessment of Vital Signs
- Physical Examination
- Assessment of Local Application Site Reactions
- Visual Inspection of EAWs
- Study Drug Return and Accountability
- Urine Pregnancy Test
- For prematurely discontinuing subjects record reason for discontinuation.

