8.1 Subject Population/Data Sets to Be Evaluated

The subject populations are defined as follows:

- 1. Safety Population: The safety population includes all randomized subjects who received and used study product.
- 2. **Modified Intent-to-Treat (mITT) Population:** A modified intent-to-treat population includes all subjects who are randomized, applied at least one dose of assigned product, and returned for at least one post-baseline evaluation visit.
- 3. **Per Protocol (PP) Population:** all randomized subjects who met all inclusion/exclusion criteria, had no protocol violations that would affect the treatment evaluation, were compliant with applying study product, and returned to the study site for the primary endpoint evaluation at four days (± 5 days) after the last day of the last cycle of treatment. Compliant subjects are defined as those who used at least 75% and no more than 125% of study drug doses until treatment success or four cycles of treatment.

Subjects discontinuing due to "treatment failure" will be included in the PP population analysis as treatment failures, and will have alternative treatment recommended by the Investigator. Subjects discontinued prematurely from the study for any other reason (i.e., noncompliance, or withdrawal of consent, etc.) will be excluded from the PP population, but included in the mITT population, using Last Observation Carried Forward (LOCF).

The results in the PP population will be considered definitive for therapeutic equivalence with those in the mITT population considered supportive. The results in the mITT population will be considered definitive

Confidential Page 46 of 59

for superiority of each active treatment to placebo with those in the PP population considered supportive. Safety analyses will be performed using the Safety population.

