3.1 Study Overview

Clinical study of protocol 016-POD-001 is a multicenter, parallel group, randomized, doubleblind, placebo-controlled, trial with clinical endpoint comparing Podofilox Topical Gel 0.5% to Condylox[®] Gel 0.5% and a matching placebo. The study will be conducted in adult male and female patients with external anogenital warts. The study also assesses comparative safety of Podofilox Topical Gel 0.5% and Condylox[®] Gel 0.5%.

Safety data analysis will include local application site reaction scores (erythema, dryness, burning/stinging, erosion, edema, pain, itching and bleeding), reported adverse events, vital signs and concomitant medication assessments summarized by treatment group and time point of collection, when appropriate.

The primary objective is to compare the clinical efficacy among patients with anogenital warts when treated with Podofilox Topical Gel 0.5% versus Condylox[®] Gel 0.5% and placebo. The secondary objective is to demonstrate safety of Podofilox Topical Gel 0.5% compared to Condylox[®] Gel 0.5% and placebo assessed by the frequency and severity of adverse events, and application site reaction scores (erythema, dryness, burning/stinging, erosion, edema, pain, itching, and bleeding).

The planned overall sample size for this clinical trial is approximately 413 adult male and female patients with external anogenital warts, who will be randomized at a 3:3:1 ratio (test: RLD: placebo) at about 16 clinical research centers in the United States, Russia and Ukraine. The mITT and PP population sizes will be approximately 392 and 350, correspondingly. A subject is considered enrolled after he/she has provided a signed informed consent and begins the screening process. A subject is considered randomized upon receiving his/her randomized treatment assignment.

Confidential

The entire study will consist of a maximum of 6 visits:

- 1. Visit 1 (Day -14 up to -1): Screening Evaluations at the Study Site performed.
- 2. Visit 2 (Day 0): Study Drug Dispensation.
- 3. Visit 3-5 (Day 7 ±1 [Week 1], Day 14 ±1 [Week 2], and Day 21 ±1 [Week 3]: Follow-up of the Study Drugs.
- 4. Visit 6 (Day 28 ± 5 [Week 4]): End of Study Visit / Early Termination Visit at the Study Site including Safety and Efficacy Evaluation.

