7.5.6 Per-Protocol (PP) Population

All randomized subjects who met all inclusion/exclusion criteria, had no protocol violations that would affect the treatment evaluation , were compliant with applying study product, and returned to the study site for the primary endpoint evaluation at 4 days (\pm 5 days) after the last day of the last cycle of treatment. Compliant subjects are defined as those who used

Protocol: 16-POD-001 Version 2.0, 15-Jan-2018

Confidential

at least 75% and no more than 125% of study drug doses until treatment success or four cycles of treatment.

Subjects discontinuing due to "treatment failure" will be included in the PP population analysis as Treatment Failures and will have alternative treatment recommended by the Investigator.

The results in the PP population will be considered definitive for therapeutic equivalence and those in the mITT population considered supportive. The results in the mITT population will be considered definitive for superiority analysis of each active treatment to placebo and those in the PP population will be considered supportive. Safety analyses will be performed using the Safety population.

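### The Visit 6 and primary endpoint window (Day 28 ±5) includes cycle 4 dosing Days 23 and 24, so a final failure can be scored before dosing is complete; the effect is probably small

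*Protocol*

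**What the plan says.** - **Dosing.** Protocol 3.1 sets two applications a day for three days, then four days of rest, for up to four cycles: "Study drug will thus be applied only on Days 1, 2, 3, 8, 9, 10, 15, 16, 17, 22, 23 and 24". Its intended visit timing is "Study visits will occur on the seventh (7) day of each treatment cycle", which for cycle 4 is Day 28.
- **Endpoint window.** Protocol 8.1 admits to PP those who returned for the "primary endpoint evaluation at four days (± 5 days) after the last day of the last cycle of treatment". Protocol 8.3.2 and SAP 9.1 use the same timing, and SAP 7.5.6 requires that subjects "returned to the study site for the primary endpoint evaluation at 4 days", with the same ±5.
- **Visit window.** Protocol 6.3.4, Appendix B and SAP 7.6.3 put the last visit at Day 28 ±5. SAP 3.1 lists "Visit 6 (Day 28 ± 5 [Week 4]): End of Study Visit".
- **Scoring.** Under protocol 6.3.4, if success "has not been achieved through the EOS/ET visit (Day 28±5 [Week 4]), then the subject will be considered" a treatment failure, and end-of-study activities follow.
- **Compliance.** Protocol 5.8 counts as compliant those who "completed at least 75% and no more than 125% of study drug applications until treatment success or for a maximum of four cycles".
- **After Visit 6.** No later wart assessment is scheduled. Appendix B shows drug return and no dispensing at Visit 6.

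**The concern.** The window opens one day before the last planned dose. Visits 3 to 5 (±1 day) always fall at least three days after the last planned dose of their cycle. Only the visit that fixes a final failure can come before dosing ends.

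An uncleared subject seen on Day 23 or 24 is inside the window, so the visit is not a deviation as the text stands. The result enters PP, which decides equivalence, and mITT, which decides superiority. A wart that would have gone after the remaining doses or the rest days is recorded as a failure. If both arms lose the same share of successes, a true difference shrinks slightly. If late clearance differs by arm, the observed difference can move either way.

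**Working it through.** **1. The plan's own figure.** SAP 5.3 gives 0.92 as the probability of equivalence, with 40% success in both active arms, 150 per arm in PP, limits ±0.20 and a continuity-corrected 90% Wald interval.
- se = √(2 × 0.40 × 0.60 / 150) = 0.0566; continuity term = (1/150 + 1/150)/2 = 0.00667.
- Power = 2Φ((0.20 − 0.00667)/0.0566 − 1.645) − 1 = 0.924. The exact binomial sum gives 0.928. The figure reproduces.

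**2. The calendar.**
- Endpoint window: 24 + 4 − 5 = Day 23 to 24 + 4 + 5 = Day 33.
- Visit 6: 28 − 5 = Day 23 to 28 + 5 = Day 33. The two windows are the same.
- Overlap with dosing days: Days 23 and 24, which are 2 of 11 permitted days.
- Taking the last day of the last cycle as Day 28 would give Days 27 to 37. That contradicts the explicit Day 28 ±5.

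**3. The compliance rule.** Planned applications total 2 × 3 × 4 = 24, of which 18 precede cycle 4.
- Day 23 visit: 20 or 21 of 24 used (83.3% or 87.5%).
- Day 24 visit: 22 or 23 of 24 used (91.7% or 95.8%).
- With no cycle 4 dose at all: 18/24 = 75.0%, which still passes.

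**4. Size.** The documents give neither the frequency of early visits nor clearance by cycle, so both inputs are assumptions:
- e = share of late-clearing subjects seen on Days 23–24, taken as 2% to 10%;
- s = share of an arm's successes that clear only after that, taken as 20% to 50%;
- share of successes lost: L = e × s, from 0.4% to 5%.

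False equivalence is the exact binomial probability that the planned interval lies within ±0.20 when the true rates are 40% and 20%, with n = 150 per arm. With equal L in both arms the rates become 0.40(1 − L) and 0.20(1 − L):

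| L | P(equivalence declared) |
|---|---|
| 0 | 3.78% |
| 0.4% | 3.91% |
| 1% | 4.12% |
| 2.5% | 4.66% |
| 3% | 4.86% |
| 5% | 5.70% |

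The 5% level is reached at L = 3.35%, which is 0.0335 × 60 ≈ 2 successes in the 40% arm and 0.0335 × 30 ≈ 1 in the 20% arm. With s = 50% this needs e = 0.0335/0.50 = 6.7%. With s = 20% it needs 0.0335/0.20 = 16.8%, beyond the assumed range.

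Starting from 50% and 30% instead, the baseline is 3.9%, and 5% lost gives 5.7%. A figure of 9.4% needs L = 12.5%, for example a quarter of subjects seen early and s = 50%.

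Unequal s, at e = 10%:
- s = 20% in the better arm and 50% in the worse: 0.40 × 0.98 = 0.392 and 0.20 × 0.95 = 0.190, difference 0.202, P = 3.5%.
- The reverse: 0.40 × 0.95 = 0.380 and 0.20 × 0.98 = 0.196, difference 0.184, P = 7.2%.

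Power when the arms are truly equal hardly moves: 0.928 at 40% in each, 0.933 at 38% (L = 5%).

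**The case against.** The strongest reply is that this will seldom happen. Visits belong on the seventh day of the cycle, and cycle 4 drug is handed out around Day 21. A Visit 6 on Day 23 or 24 means a site closing a subject out within days of starting the last cycle. This stands. A reader might infer from 2 of 11 permitted days that about 18% of final visits fall on dosing days. The documents do not support that, because nothing suggests that visits spread evenly over the window.

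Safeguards also exist. The endpoint wording shows that a post-treatment assessment was intended. PP excludes violations that would affect the evaluation, and a meeting before lock sets the population flags (SAP 7.5.3). Listings 16.2 and 16.3.4 show visit and application dates, so these subjects can be found. This stands in part: exclusion would be discretionary, because an in-window visit breaks no stated rule.

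Two practical points stand. The SAP cites a Note to File dated 27 Feb 2019, so a window change may come too late. Protocol 1.3 also says that the design follows an FDA draft guidance, and whether the ±5 comes from it cannot be seen here. Neither point bears on a sensitivity run.

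Protocol 6.3.3 lists dispensing for Visits 3 to 6, against Appendix B. That leaves open whether a subject might go on dosing after an early Visit 6, but it changes nothing here, since no later assessment would be scheduled.

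**Conclusion.** The point holds as a minor one. Under the stated rules, a subject can be scored a final failure in PP and mITT on Day 23 or 24, before cycle 4 dosing is complete, and no fixed rule removes that subject from PP.

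A reader might go further and infer that the equivalence test is biased towards success or that its error rate is above 5%. The documents do not support that. With equal loss in both arms, false equivalence passes 5% only if about 3.4% or more of successes are lost; with e = 5% it stays at or below 4.7%. The 7.2% figure needs e = 10% together with opposite extremes of late clearance in the two arms, and the mirror case falls to 3.5%. All of these figures rest on assumed e and s. The direction is unknown and the size is probably small. The case for acting is that the remedy is cheap.

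**What to change.** **Main change, before database lock.** Add to SAP 9.1.1 one PP sensitivity run of the equivalence interval. Exclude, whatever the outcome, every subject whose scheduled Visit 6 (not an early termination visit for worsening) fell on or before the third scheduled dosing day of cycle 4. Date that day from the subject's actual first cycle 4 application (Listing 16.3.4), not from a fixed Day 24. If Visit 5 falls on Day 22, which is allowed, cycle 4 may start on Day 23 and dosing end on Day 25, and a fixed cutoff would miss a Day 25 visit. Where no cycle 4 application is recorded, use Day 24. Report the number excluded by arm, as a repeat of Table 14.2.2.1.1. If it is zero, the question closes.

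Cost: one extra analysis from dates already collected. If 2%, 5% or 10% of PP subjects were excluded (147, 142 or 135 per arm), its power at 40% in both arms would be 0.917, 0.905 or 0.884, so it stays informative.

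**If visits are still to be scheduled.** Also open the Visit 6 window at Day 25 (Day 28 −3/+5) and at least one day after that third dosing day. Subjects who clear at Visits 3 to 5 are unaffected: Days 6–8, 13–15 and 20–22 fall 3 to 5 days after dosing Days 3, 10 and 17. Amend protocol 6.3.4, 8.1, 8.3.2 and Appendix B, SAP 7.5.6, 7.6.3 and 9.1, and the places that repeat the window (both synopses, protocol 8.2, SAP 3.1, 3.2 and 6). Cost: 2 of 11 scheduling days, and a few more out-of-window visits.

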3.2 Number of Subjects and Sites

The planned overall sample size for this clinical trial is approximately 413 adult male and female patients with external anogenital warts, who will be randomized at a 3:3:1 ratio (test: RLD: placebo) at about 16 clinical sites in the United States, Russia and Ukraine.

Confidential Page 26 of 59

4 SELECTION AND WITHDRAWAL OF STUDY POPULATION

4.1 Eligibility Criteria

Subjects who satisfy **ALL** of the following **inclusion** and have **NONE** of the following **exclusion** criteria may be enrolled in the study:

4.1.1 Inclusion Criteria

- 1. Willing and able to provide written informed consent prior to participating in this study.
- 2. Male or female subjects, aged 18-65 inclusive, with a clinical diagnosis of external anogenital warts (i.e., perianal warts and/or external genital warts), including two or more distinct external genital warts, and wart area that is equal or less than 10 cm². Histological confirmation should be obtained if there is any doubt of the diagnosis.
- 3. Females of childbearing potential may be enrolled if they practice a method of birth control with a reliability of at least 90%.
- 4. Sexually active study participants must agree to abstain from sexual activity of any kind throughout the treatment period to prevent cross- and reinfection by HPV.
- 5. Any female subject with childbearing potential has a negative urine pregnancy test at Baseline.
- 6. Negative HIV test within 4 weeks before Baseline.

